#### 5.4.8 Other Safety Analyses

Comprehensive neurological examination results will be summarized by visit for treatment group by core study treatment (placebo and elenbecestat total) and combined total.

Dermatology findings will be presented in subject data listing.

Cognitive decline will be assessed as a safety assessment, in addition to efficacy assessments. Cognitive assessments will include MMSE.

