## 5.4 Safety Analyses

Safety analysis will be performed similarly to the Core Study. All safety analyses will be based on OLE-SAS. The incidence of AEs, out-of-normal-range laboratory safety test variables, abnormal ECG findings, out-of-range vital signs, suicidality (Columbia Suicide Severity Rating Scale(C-SSRS)), and changes from baseline in laboratory safety test variables, ECGs, safety MRI, vital sign measurements, and cognitive decline assessment such as MMSE will be summarized by using descriptive statistics. The OLE baseline is used for all safety analyses.

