#### 5.4.4 Laboratory Values

Laboratory results will be summarized using Système International (SI) units, as appropriate. For all quantitative parameters, the actual value and the change from baseline to each post-baseline visit will be summarized by visit for treatment group by core study treatment (placebo and elenbecestat total) and combined total using descriptive statistics. The end of treatment visit and 12 week Follow-up visit are also included, as appropriate. Qualitative parameters will be summarized using frequencies (number and percent of subjects), and changes from baseline to each post-baseline visit will be reported using shift tables. Percentages will be based on the number of subjects with both non-missing baseline and relevant post-baseline results.

Laboratory test results will be assigned a low/normal/high (LNH) classification according to whether the value was below (L), within (N), or above (H) the laboratory parameter's reference range. Within-treatment comparisons for each laboratory parameter will be based on 3-by-3 tables (shift tables) that compare the baseline LNH classification to the LNH classification at each post-baseline visit and at the end of treatment visit and 12 week Follow-up visit.

The Sponsor's Grading for Laboratory Values ([Appendix 13.1](#)) presents the criteria that will be used to identify subjects with treatment-emergent markedly abnormal laboratory values (TEMAV). Except for phosphate, a TEMAV is defined as a post-baseline value with an increase from baseline to a grade of 2 or higher. For phosphate, a TEMAV is defined as a post-baseline value with an increase from baseline to a grade of 3 or higher. The incidence of TEMAVs will be summarized for treatment group by core study treatment (placebo and elenbecestat total) and

combined total. When displaying the incidence of TEMAVs, each subject will be counted once in the laboratory parameter high and low categories, as applicable.

Lymphocyte subset parameters (ie, CD4 [T helper cells], CD8 [cytotoxic T cells], CD19 [B cells], CD16/CD56 [natural killer cells] and CD14 [macrophages], and regulatory T cells) will be summarized in the same manner as other laboratory parameters.

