#### 5.4.6 Electrocardiograms

Descriptive statistics for ECG parameters and changes from baseline will be presented by visit for treatment group by core study treatment (placebo and elenbecestat total) and combined total. Shift tables will present changes from baseline in ECG interpretation (categorized as normal; abnormal, not clinically significant; abnormal, clinically significant) to each post-baseline visit and to the end of treatment visit and the 12 week Follow-up visit.

In addition, the number (percentage) of subjects with at least 1 post-baseline abnormal ECG result in QTcF during the treatment period will be summarized. Clinically abnormal ECG results in QTcF will be categorized as follows:

Absolute QTcF interval prolongation:

- QTcF interval >450 msec

- QTcF interval >480 msec
- QTcF interval >500 msec

Change from baseline in QTcF interval:

- QTcF interval increases from baseline >30 msec
- QTcF interval increases from baseline >60 msec

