#### 5.4.7 Safety MRI

Vasogenic Edema and white matter disease will be summarized by visit for treatment group by core study treatment (placebo and elenbecestat total) and combined total. Shift table for the total number of microhemorrhages will be presented by visit for treatment group by core study treatment (placebo and elenbecestat total) and combined total. Other abnormalities will be presented in subject data listing.

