## 8 DEFINITIONS AND CONVENTIONS FOR DATA HANDLING

### 8.1 Definition of baseline

The OLE baseline value is defined as the most recent value reported just before first dosing in OLE (for safety, efficacy and PD).

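### SAP Section 5.4.8 tabulates neurological examination results by visit only, so the planned summary does not show how many subjects developed a new finding relative to OLE baseline

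*SAP*

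**What the plan says.** SAP Section 5.4.8 gives the neurological examination one sentence: "Comprehensive neurological examination results will be summarized by visit for treatment group by core study treatment", with placebo and elenbecestat total as the groups, plus a combined total. It names no shift table, change from baseline or count of new or worsened findings.

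Section 5.4 lists what will be compared with baseline: "changes from baseline in laboratory safety test variables, ECGs, safety MRI, vital sign measurements, and cognitive decline assessment such as MMSE". The neurological examination is not in that list. The same section adds: "The OLE baseline is used for all safety analyses". Section 8.1 defines the reference: "The OLE baseline value is defined as the most recent value reported just before first dosing in OLE".

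Some other categorical safety results do get a within-subject comparison:
- Qualitative laboratory results (Section 5.4.4): "changes from baseline to each post-baseline visit will be reported using shift tables". The low/normal/high classes are also cross-tabulated against baseline.
- ECG (Section 5.4.6): "Shift tables will present changes from baseline in ECG interpretation", carried through to the end of treatment and 12 week Follow-up visits.
- Microhemorrhages (Section 5.4.7): "Shift table for the total number of microhemorrhages will be presented by visit".

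Others do not. Section 5.4.7 summarizes vasogenic edema and white matter disease by visit, and Section 5.4.5 gives frequency counts of clinically notable vital signs.

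**The concern.** The primary objective is long-term safety and tolerability in subjects with MCI or dementia due to AD. Every subject in the extension receives the same open-label dose, and the reporting groups are defined by Core Study treatment. There is no concurrent untreated group, so comparing each subject with his or her own OLE baseline is the main way to see change on treatment.

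For an examination finding, the useful quantity is the number of subjects who acquired a new sign, or whose sign worsened, after the first OLE dose. A by-visit percentage does not give this. It mixes findings already present at OLE baseline with new ones, and a resolved finding offsets a new one. A reader of the study report could see a flat line of percentages and take it as evidence that nothing happened.

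**Working it through.** The SAP gives no examination rates and Section 4 gives no sample size, so there is no figure to reproduce. The check has three steps. All numbers in steps 1 and 2 are assumed for illustration.

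**Step 1. What by-visit counts determine.** Let n subjects be examined at both times, with a abnormal at OLE baseline and b abnormal at a visit. The number newly abnormal then lies between max(0, b − a) and min(b, n − a).

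| n | a | b | Lower bound | Upper bound |
|---|---|---|---|---|
| 100 | 20 | 20 | max(0, 0) = 0 | min(20, 80) = 20 |
| 100 | 20 | 25 | max(0, 5) = 5 | min(25, 80) = 25 |
| 100 | 30 | 30 | max(0, 0) = 0 | min(30, 70) = 30 |

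In each row the range is wide, and the by-visit table cannot narrow it. A 2 × 2 shift table from the same data gives the number exactly.

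**Step 2. One case within the third row.** Of 100 subjects, 30 are abnormal at baseline. At the visit, 7 of those 30 are recorded as normal and 7 of the other 70 are newly abnormal.
- Prevalence at the visit: (30 − 7 + 7)/100 = 30%, the same as at baseline.
- New findings among those normal at baseline: 7/70 = 10%.
- If the 7 new cases had left before that visit, the scheduled-visit row would show (30 − 7)/(100 − 7) = 23/93 = 24.7%, an apparent improvement.
- If their last examination were carried into a separate end-of-treatment row, as Section 8.3 allows, that row would return to (23 + 7)/100 = 30%. The subjects are recovered, but the row still shows prevalence and not the 10%.

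The 7 and 7 were chosen to cancel exactly. The case shows what can happen and does not estimate what will happen in this trial.

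**Step 3. Which examinations reach the table.** Section 8.3 selects one assessment per analysis visit: first the one closest to the target day, then scheduled over unscheduled, then the earliest. An unscheduled examination prompted by a new symptom loses to a scheduled one nearer the target day, or equally near it. If the sign has gone by the scheduled examination, the by-visit table never shows it.

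**The case against.** There is a fair case that little is lost, and parts of it stand.

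- *New signs are captured elsewhere.* Section 5.4.2 defines treatment-emergent adverse events as events that are new, re-emerged or worsened relative to OLE baseline, and tabulates them in several ways. This stands, so a reader who infers that new signs cannot be distinguished from old ones goes too far. The route does depend on the investigator reporting the sign as an adverse event. Laboratory and ECG abnormalities have the same route, and the SAP still gives them shift tables.
- *The examination is not singled out.* A reader might infer that it alone departs from the plan's method. It does not: vasogenic edema and white matter disease are also summarized by visit only, and dermatology findings are only listed.
- *Subjects who leave are not lost.* Section 8.3 assigns Last on treatment, End of treatment and 12 week Follow-up visits for safety endpoints, and Section 3.2 requires an Early Discontinuation Visit. An inference that a subject with a new sign disappears on leaving is therefore unsupported, provided the examination is done at those visits and they are shown in this table. Step 2 shows that these rows still report prevalence.
- *The OLE baseline applies to all safety analyses.* This fixes which baseline to use when a comparison is made. It does not call for a comparison.
- *The table shells are separate (Section 11).* They may show a baseline row or more. A baseline row alone would not give within-subject change, and the SAP states the shift analysis in its own text for the other measures.
- *The examination is not named among the primary endpoints in Section 5.1.1, and analyses were reduced after termination.* True, and this limits the weight of the point. The reductions listed in Section 7 concern efficacy and biomarker analyses, not safety.

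**Conclusion.** The point holds as an under-specified and less informative summary. The only analysis of the neurological examination that Section 5.4.8 commits to does not give the number of subjects with a new finding relative to OLE baseline, and the window rule can hide an unscheduled examination that shows one. The documents do not support reading it as lost information: the subject-level records still allow the comparison, and signs reported as adverse events are counted against OLE baseline.

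The effect in this trial cannot be estimated, because the SAP gives no baseline prevalence, no rate of new findings and no number of subjects. The illustrations rest on assumed counts. They establish only that the by-visit percentages are compatible with very different numbers of new cases. No conclusion of the plan turns on this, since all analyses are descriptive. It is a cheap improvement to a safety summary in an uncontrolled extension, and worth making.

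**What to change.** Keep the by-visit summary in Section 5.4.8 and add two items.

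1. A shift table from OLE baseline to each post-baseline visit, End of treatment and 12 week Follow-up, by the same groups and combined total, as is done for ECG interpretation. Use the categories recorded on the eCRF. The SAP does not say how the results are coded, so a normal/abnormal split for each component should not be presumed.
2. The number (percent) of subjects with at least one new finding at any post-baseline examination, scheduled or unscheduled, among subjects with an OLE baseline examination. Include worsened findings if the eCRF records severity. State that this count uses all post-baseline examinations and is not subject to the one-assessment-per-window selection in Section 8.3.

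Section 5.4 should then add the neurological examination to the measures compared with baseline. The cost is a few lines of SAP text, matching shells and some extra table programming. The amount depends on how many examination components are recorded. The tables would draw on examination data already due to be summarized.

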### 5.5 Efficacy Analyses

There is no primary efficacy analysis for this study. Secondary analyses will be based on OLE-FAS as specified in [Section 5.2.1](#). The analyses using OLE baseline are summarized by treatment group by core study treatment (placebo, elenbecestat 50 mg R, elenbecestat 50 mg Total) and combined total. Elenbecestat 50 mg R group are the subjects initially randomized to 50 mg group in Core Study. Elenbecestat 50 mg Total group are the subjects ever exposure to 50 mg in Core Study.

#### 5.5.1 Primary Efficacy Analyses

There is no primary efficacy endpoint.

#### 5.5.2 Secondary Efficacy Analyses

The secondary efficacy endpoints in this SAP are:

- Change from OLE baseline in MMSE and FAQ scores
- Change / percent change from OLE baseline in total hippocampal volume, left and right hippocampal volume, whole brain volume, and total ventricular volume with up to 24 and 48 months as measured by vMRI

The actual value and change (percent change, if applicable) from baseline will be summarized using descriptive statistics for OLE baseline. Due to the termination of the study, the summary statistics will not be presented graphically.

Due to the termination of the study, the relationship between efficacy endpoints and biomarker endpoints will not be explored using correlation analysis.

### 5.5.3 Other Efficacy Analyses

No other efficacy analyses are planned for this study

## 5.6 Pharmacokinetic, Pharmacodynamic, Pharmacogenomic, and Other Biomarker Analyses

The OLE PD Analysis Set will be used for the summaries and analyses of PD biomarkers. The same summary groups as for efficacy are used for PD analyses.

### 5.6.1 Pharmacokinetic Analyses

Not applicable.

### 5.6.2 Pharmacodynamic, Pharmacogenomic, and Other Biomarker Analyses

The secondary endpoint from PD marker in this SAP is:

- Percent Change from baseline in plasma amyloid measurements

The actual value and percent change from OLE baseline will be summarized using descriptive statistics for OLE baseline. Due to the termination of the study, the summary statistics will not be presented graphically.

## 5.7 Other Analyses

No other analyses are planned.

## 6 INTERIM ANALYSES

No interim analyses in OLE phase.

## 7 CHANGES IN THE PLANNED ANALYSES

Due to the termination of the study, the following analyses, as described in the protocol, will not be performed.

- Summary statistics of change from Core Study baseline in MMSE, FAQ, vMRI parameters, and PD biomarkers
- Figures of change from baseline in MMSE, FAQ, vMRI parameters, and PD biomarkers
- Correlation analysis for the relationship between efficacy endpoints and biomarker endpoints

---

## 8 DEFINITIONS AND CONVENTIONS FOR DATA HANDLING

### 8.1 Definition of baseline

The OLE baseline value is defined as the most recent value reported just before first dosing in OLE (for safety, efficacy and PD).

### 8.2 Algorithms for Efficacy Parameters

This section describes each efficacy parameter, in particular, the algorithms and missing data handling procedure to derive the totals scores if applicable.

**FAQ:** The Functional Assessment Questionnaire (FAQ) is composed of 10 activities. Each activity is rated as 0 = Normal, 1 = Has difficulty but does by self, 2 = Requires assistance, 3 = Dependent, 8 = Not Applicable. The Total Score is the sum of the 10 activities. If any activity is missing then the Total Score is missing. Activities marked as “Not Applicable”, are not use in the computation of the Total Score. However, in order to account for “Not Applicable” activity(s), the Total Score is weighted as follows;

Total Score = Total Score x 30 / (30 minus 3 times the number of activities marked “Not Applicable”)

**ISLT:** The International Shopping List Task (ISLT) is a verbal learning and episodic memory test assessing both immediate and delayed recall. Number of correct responses is used as the score in both tests and transformed to Z-score, respectively.

**CBB:** The CogState Brief Battery (CBB) is a computer-based battery comprising 4 cognitive tests:

Detection – a simple reaction time test. Speed of response is the measure.

Identification – a simple choice reaction time test. Speed of response is the measure.

One Card Back – a simple working memory test. Accuracy of response is the measure.

One Card Learning – a visual learning and memory test. Accuracy of response is the measure.

**CDR:** The Clinical Dementia Rating (CDR) scale is a clinical global rating scale requiring the interviewing of both the subject and an informant who knows and has contact with the subject. The CDR is a clinician-directed assessment of both cognition and function, and is intended to capture the state and therefore the disease stage of the individual. The CDR assesses 6 domains of subject function; memory, orientation, judgment and problem solving, community affairs, home and hobbies, and personal care. Each of these items has a maximum possible score of 3 points and the total score is a sum of the item scores (sum of boxes) giving a total possible score of 0 to 18 with higher scores indicating more impairment.

**MMSE:** The Mini Mental State Examination (MMSE) is a cognitive instrument commonly used for screening purposes, for staging of disease severity and is often measured longitudinally in AD clinical studies to follow disease progression and treatment effects. MMSE is composed of 30 questions grouped into domains. For each of the MMSE domains add the correct responses. If a domain has missing data then the domain is missing. From the domains compute the six items as show in Table 3. If any domain is missing then the item is missing. The MMSE Total Score (range 0 to 30) = sum of the six items. If any item score is missing then the Total Score is missing.

**Table 3: MMSE Domains and Items**

Domain	Score Range	Item	Score Range
1. Orientation to Time	0 to 5	1. Orientation to Time	0 to 5
2. Orientation to Place	0 to 5	2. Orientation to Place	0 to 5
3. Registration	0 to 3	3. Registration	0 to 3
4. Attention and Calculation a	0 to 5	4. Attention and Calculation	0 to 5
5. Recall	0 to 3	5. Recall	0 to 3
6. Naming	0 to 2	6. Language (Sum of Naming, Repetition, Comprehension, Reading, Writing, and Drawing)	0 to 9
7. Repetition	0 to 1		
8. Comprehension	0 to 3		
9. Reading	0 to 1		
10. Writing	0 to 1		
11. Drawing	0 to 1		
		Total Score	0 to 30

a Spell WORLD Forward, then Backward score is only used if Attention and Calculation score is not available

**ADAS-cog14**: The Alzheimer’s Disease Assessment Scale - Cognitive subscale (14 items) (ADAS-cog14) is composed of 14 items, see Table 4.

**Table 4: ADAS-cog14 Items and Algorithm for derivation of Item Scores and Total Score**

Item	Algorithm	Handling Missing Data	Score Range
1. Word Recall	Total the number of “No” responses for each trial. The subscore is the sum the scores from trials 1, 2, and 3, divide by 3.	If a trial is missing or partially done then trial score is missing. If a trial score is missing then the subscore is missing	0 to 10
2. Commands	Total the number of “No” responses from the 5 tasks	If any task is missing then the subscore is missing	0 to 5
3. Constructional Praxis	Count the number of “No” responses. The subscore is 0 = all 4 drawings correct 1 = 1 figure drawn incorrectly 2 = 2 figures drawn incorrectly 3 = 3 figures drawn incorrectly 4 = 4 figures drawn incorrectly 5 = no figures drawn, scribbles, parts of forms	If any task is missing then the subscore is missing	0 to 5
4. Delayed Word-Recall	Total the number of “No” responses.	If any response is missing then subscore is missing	0 to 10
5. Naming Objects / Fingers	Total the number of “No” responses. The subscore is 0 = 0-2 “no” responses 1 = 3-5 “no” responses 2 = 6-8 “no” responses 3 = 9-11 “no” responses 4 = 12-14 “no” responses 5 = 15-17 “no” responses	If any response is missing then subscore is missing	0 to 5
6. Ideational Praxis	Total the number of “No” responses.	If any response is missing then subscore is missing	0 to 5
7. Orientation	Total the number of “No” responses.	If any response is missing then subscore is missing	0 to 8
8. Word Recognition	For each trial, total the number of “1” responses. If the total is 12 or less, then the trial score = total. If the total is > 12 then trial score=12. The subscore is the sum the scores from trials 1, 2, and 3, divide by 3.	If a trial is missing or partially done then trial score is missing. If a trial score is missing then the subscore is missing	0 to 12
9. Remembering Test	The subscore is	If the response is	0 to 5

Instructions	0= None, 1= Very Mild, 2= Mild, 3= Moderate, 4= Moderately Severe, 5= Severe	missing then subscore is missing															
10. Comprehension	The subscore is 0= None, 1= Very Mild, 2= Mild, 3= Moderate, 4= Moderately Severe, 5= Severe	If the response is missing then subscore is missing	0 to 5														
11. Word Finding Difficulty	The subscore is 0= None, 1= Very Mild, 2= Mild, 3= Moderate, 4= Moderately Severe, 5= Severe	If the response is missing then subscore is missing	0 to 5														
12. Spoken Language Ability	The subscore is 0= None, 1= Very Mild, 2= Mild, 3= Moderate, 4= Moderately Severe, 5= Severe	If the response is missing then subscore is missing	0 to 5														
13. Executive Function (Maze)	The subscore is based on the total number of seconds to complete the task and/or whenever the task was stopped due to 2 errors being made, as follows;  0 = 0-30 seconds 1 = 31-60 seconds 2 = 61 – 90 seconds 3 = 91 – 120 seconds 4 = 121-239 seconds 5 = 240 seconds or at least 2 errors	If the response is missing then the subscore is missing	0 to 5														
14. Number Cancellation	Adjusted Score = Total # correct targets crossed off minus Total # incorrect targets crossed off minus Total # times reminded of task. Then use Adjusted Score to determine the subscore as follows;  
  
 Adjusted Score	Subscore	
   
 ≥23	= 0	
 
 18-22	= 1	
 
 13-17	= 2	
 
 9-12	= 3	
 
 5-8	= 4	
 
 ≤4	= 5	
  
	Adjusted Score	Subscore	≥23	= 0	18-22	= 1	13-17	= 2	9-12	= 3	5-8	= 4	≤4	= 5	If any component of the adjusted score is missing then the subscore is missing	0 to 5
Adjusted Score	Subscore																
≥23	= 0																
18-22	= 1																
13-17	= 2																
9-12	= 3																
5-8	= 4																
≤4	= 5																
Total Score	Total Score = sum of the subscores above	If any subscore is missing then Total Score is missing	0 to 90														

